*** REDcap URL: <https://redcap.vanderbilt.edu/> ***

SUBJECT ID'S

- ID's will have a 1 or 2 at the end, unlike our assigned subject numbers. This is fine—we will resolve this before final export (see “Dual Entry and Reviewing” below)

DATA ENTRY ROLES

[figure not shown]
- Enterer 1=first entry
- Enterer 2: second entry
- Reviewer(s): compare double entry for accuracy and can act as either Enterer 1 or Enterer 2
 - To act as an enterer, add --1 or --2 to the end of the Record ID when entering a new Record ID. This assigns the record to either Enterer 1 or 2, respectively

[figure not shown]
The image shows a screenshot of a REDCap interface. At the top, there is a dropdown menu labeled "Choose an existing Record ID" with the option "-- select record --". Below this, there is an input field labeled "Enter a new or existing Record ID" containing the value "STM 113--1".

DUEL ENTRY AND REVIEWING

[figure not shown]
- Once a record is entered twice, a Reviewer can compare and check the records:
- Go to “Applications” (left side of the REDcap screen), and select “Data Comparison Tool”

- Choose the desired Record ID and “Compare selected record.” REDcap will then show a list of all inconsistencies.

- Resolve inconsistencies in the records — select one or the other in the list and edit. As you go through the list, inconsistencies be displayed—even after resolution— until you select “Compare selected record” again (see next step)
- After resolving all inconsistencies, again select “Compare selected record”
- If there are no more inconsistencies, REDcap will give you the option to merge the records, thus creating **one** correct record. This is an easier way to compare than exporting first, and then comparing the spreadsheets.

**However, we are NOT yet actually merging the records. We just resolve the inconsistencies, until after all 4 visits are entered (or until NDAR submission). Then we can merge for the final record more efficiently. **

#### 4.4. Statistical Design and Power

**Post-attrition Sample Size Used to Test Aims and Compute Statistical Power.** We propose to recruit approximately 46 participants to enroll 40 participants over the first 2 years of the project with the last year being used to complete the treatment and assessment for the last wave of recruitment. Using a 10% attrition rate, which is the maximum attrition rate to date of past SENSE Theatre trials, the post-attrition sample size will be 40 (equally distributed between experimental and control groups). The analyses and power analyses are based on post-attrition sample size and past findings involving the primary dependent variables.

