**Power analyses for tests of hypothesis associated with Aim 1.** Using a one-tailed test (based on the a priori predicted direction of differences), 80% power, 5% type 1 error, and a post-attrition sample size with equal groups of 40 (20 in each group), the minimal detectable effect size is an  $R^2$  of 0.14 (i.e., standardized mean difference of .80). The effect size of the between-group difference on the pretest-adjusted posttest ERP measure of memory for faces in our most recent RCT of SENSE Theatre was an  $R^2$  of .18 (i.e., standardized mean difference of .94). Therefore, it is feasible that we will detect the predicted SENSE Theatre effect on our primary measure of memory for faces with the proposed sample size.

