**Power analyses for tests of primary dependent variable in Aim 2:** A one-tailed test of the association between memory for faces and social awareness symptoms is reasonable because past evidence indicates that association is negative and the theory predicting the association indicates that the association should be negative. Using a one-tailed test, 80% power, and 40 post-attrition sample size, the minimally-detectable effect size for the association between memory for faces and social awareness symptoms is an R square value of 0.16. In our past work, the association between ERP-measured memory for faces and SRS-measured social awareness symptom severity was  $R^2 = 0.15$ . Thus, it is feasible that we will detect the expected association between memory for faces and social awareness symptom severity with a post-attrition sample size of 40.

**Interpretative framework for findings detected in the context of multiple significance testing without alpha adjustment.** The R33 funding mechanism is designed to enable the acquisition of preliminary data to aid the design of more robust tests of the efficacy of treatments. Adjusting alpha for multiple significance testing at this early stage would increase the probability of Type II error. Therefore, the results will be considered pilot given the inflation of type 1 error resulting from using multiple significance tests to address the same aim. The pilot findings will provide the preliminary data needed to plan for a future, larger RCT.

**The aforementioned design is rigorous and the results from the analyses will set the stage to inform Go/No-Go decisions as to whether further development or testing of the intervention in a larger sample of adult participants with ASD is warranted.**

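### SAP section 4.4 gives 40 both as the number enrolled and as the number left after 10% attrition, so the number to be randomised is ambiguous; if it is 40, the Aim 1 detectable effect is d about 0.85, not 0.80

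*SAP*

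**What the plan says.** SAP section 4.4, in the paragraph on post-attrition sample size, sets out the numbers in two consecutive sentences.

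- Intake: "We propose to recruit approximately 46 participants to enroll 40 participants over the first 2 years of the project".
- Loss: "Using a 10% attrition rate, which is the maximum attrition rate to date of past SENSE Theatre trials".
- Remainder: "the post-attrition sample size will be 40 (equally distributed between experimental and control groups".

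Both power statements use the last of these. The Aim 1 power paragraph assumes "a post-attrition sample size with equal groups of 40 (20 in each group", with the settings "Using a one-tailed test (based on the a priori predicted direction of differences), 80% power, 5% type 1 error". It solves for a minimal detectable effect of R2 = 0.14, d = 0.80. It compares this with R2 = 0.18, d = 0.94 from the most recent trial of the intervention, and concludes that it is feasible that "we will detect the predicted SENSE Theatre effect on our primary measure of memory for faces with the proposed sample size". The Aim 2 power paragraph starts from "Using a one-tailed test, 80% power, and 40 post-attrition sample size" and gives a minimal detectable R2 of 0.16, next to 0.15 from past work.

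The protocol gives no sample size. It places consent and an eligibility visit (ADOS, IQ) before group assignment.

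**The concern.** The same figure is used at two stages that a non-zero loss must separate. If 40 are enrolled and 10% are lost, 36 remain. If 40 remain, more than 40 must have entered.

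The text does not say whether the step from 46 to 40 is screening loss before randomisation or attrition after it. Either is possible, because people who consent can still fail eligibility before being assigned to a group. On the screening reading, the 46 is used up before randomisation and nothing is set aside for attrition.

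What is at stake is the sample size behind both power statements. The Aim 1 conclusion refers to the proposed sample size, and that phrase has no single meaning while 40 carries two. A team that took 40 as its randomisation target would need no dropout at all to analyse 40.

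**Working it through.** **Inputs.** About 46 recruited, 40 enrolled, 10% attrition and 40 post-attrition with equal arms (SAP 4.4). One-sided 5%, 80% power, d = 0.80 and R2 = 0.14, earlier-trial d = 0.94 (SAP Aim 1 power paragraph). R2 = 0.16 and past-work R2 = 0.15 (SAP Aim 2 power paragraph).

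**Step 1: the counts.**
- 40 randomised: 40 x 0.90 = 36, or 18 per arm.
- Needed to leave 40: 40 / 0.90 = 44.4, so 45, or 46 with equal arms (44 x 0.90 = 39.6; 46 x 0.90 = 41.4).
- 46 randomised: 41.4 expected, taken as 41 (20 + 21). With independent 10% losses, the chance that at least 40 of 46 remain is 0.83. The chance that all 40 of 40 remain is 0.9^40 = 0.015.

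**Step 2: reproduce the Aim 1 figure, then vary the number analysed.** Power = 1 - F(t; df, delta), where F is the noncentral t distribution function, df = N - 2, t is the one-sided 5% critical value, and delta = d x sqrt(n1 n2 / (n1 + n2)). R2 = d^2 / (d^2 + 4).

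| Analysed | delta at d = 0.80 | Power at d = 0.80 | Detectable d at 80% power | R2 | Power at d = 0.94 |
|---|---|---|---|---|---|
| 20 + 20 (as stated) | 0.80 x sqrt(10) = 2.53 | 79.9% | 0.801 | 0.138 | 89.9% |
| 20 + 21 (46 randomised) | 0.80 x sqrt(420/41) = 2.56 | 80.8% | 0.791 | 0.135 | 90.5% |
| 18 + 18 (40 randomised) | 0.80 x sqrt(9) = 2.40 | 76.0% | 0.846 | 0.152 | 86.8% |

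The top row reproduces the SAP: 80% power at d = 0.80, R2 = 0.14. Taking one more degree of freedom for the baseline covariate leaves the power figures at d = 0.80 unchanged to one decimal.

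**Step 3: Aim 2.** That paragraph does not restate alpha; I assume one-sided 5%, carried over from Aim 1. The method is not stated either, so I give a range from the Fisher z approximation to the regression noncentral t.
- R2 = 0.16: 82.4% to 85.7% at N = 40; 78.5% to 82.1% at N = 36.
- R2 = 0.15: 80.0% to 83.3% at N = 40; 75.9% to 79.5% at N = 36.
- Detectable R2 at 80% power, N = 36: 0.152 by noncentral t. By Fisher z it is tanh^2[(1.645 + 0.842) / sqrt(33)] = 0.166. The stated 0.16 lies between the two.

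**The case against.** The strongest reply is that only one loosely used verb is at fault. The paragraph is about the post-attrition sample, it says outright that this will be 40, and both power paragraphs label 40 as post-attrition. Against that stands only "to enroll 40 participants over the first 2 years of the project", with the verb left undefined. Moreover, 46 is what one would choose for equal arms and 40 completers at 10% loss. This largely stands, and it is why I take about 46 randomised as the likelier intent. That 46 to 40 is strictly a 13.0% loss (1 - 40/46) adds little, because the 46 is approximate and rounding up to equal arms explains the gap. The reply does not remove the conflict, since the text never says that 46 are randomised and screening before assignment keeps the other reading open.

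Stronger readings are tempting, but the documents do not support them:

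- **That the trial is underpowered, at 76% instead of 80%.** The SAP fixes power at 80% and solves for the effect. With 36 analysed, what changes is the detectable effect; 76.0% applies only at d = 0.80. The SAP's feasibility claim rests on d = 0.94, where power is still 86.8%.
- **That the power arithmetic is wrong.** It is right for 40 analysed.
- **That Aim 2 falls short.** At N = 36 and the stated R2 of 0.16 the range straddles 80%. At R2 = 0.15 power is about four points lower than with 40, but the SAP states no power at that value.
- **That the plan omits the number randomised.** The SAP text available here starts at section 4.4, so a statement before it cannot be excluded. Only the conflict within the paragraph is asserted.

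**Conclusion.** The paragraph is wrong as written, because 40 cannot be both enrolled and left after a 10% loss. The consequence is conditional and modest.

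- **About 46 randomised (likelier):** about 41 are expected to complete and every stated power figure holds.
- **40 randomised:** about 36 are analysed, and the Aim 1 detectable effect moves from d = 0.80 (R2 = 0.14) to about 0.85 (R2 about 0.15). The feasibility conclusion survives and no clear Aim 2 shortfall is shown.

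This rests on the SAP's own 10% attrition falling equally on both arms (to the nearest participant), the one-sided 5% test, and d read as the covariate-adjusted standardised difference. It should be corrected because both power statements depend on this number, not because the trial's case fails.

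**What to change.** Reconcile the paragraph in SAP section 4.4 according to what is intended.

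1. If about 46 are to be randomised, replace the phrase about enrolling 40 with a statement that about 46 (23 per arm) are randomised so that at least 40 are expected to complete. Leave the power figures unchanged.
2. If 40 are to be randomised, restate the post-attrition sample as 36 (18 per arm) there and in both power paragraphs, and restate the Aim 1 detectable effect as d about 0.85 (R2 about 0.15). Recheck the Aim 2 R2 of 0.16 at N = 36 by the method originally used; by the two methods above it would be 0.15 to 0.17.

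The cost is SAP wording only, with no extra enrolment. The only downside, under the second option, is a slightly less favourable stated Aim 1 figure.

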 - Watch a social and non-social stimuli and press button in response to stimuli.
 - Wear a mesh hair net type device with tiny sponges.
 - Hair will get slightly damp, but that is the only possible discomfort.
 - Intervention
 - 10 consecutive sessions for the SENSE Theatre® intervention.
 - Intervention Midpoint
 - Self- and family member/informant report questionnaires
 - Performance: at end of the SENSE Theatre® intervention.
 - Post and Follow-up Visits (Assessment, CASS, and ERP).
- Intervention will be free upon completion of all 4 parts (pre, midpoint, post, and follow-up)

- **Explain randomization:** You may be randomly assigned to either the initial study group or a waitlist control group. If you are assigned to the waitlist control group, you will still complete the study procedures, but will wait to participate in the intervention until after the initial experimental group.

VISIT SCHEDULING

General Notes:

- Add each component to Lab Calendar.
- Invite principal investigator and other involved lab members to all scheduled calendar components.
- Give reminder call/email several days before event.
- Testing must occur before ERP to ensure the facial stimuli in the ERP do not affect CMFT/WMS-III scores. Do not schedule ERP in between CFMT/WMS-III tasks.

Assessment (1-2 hours)

- **Establish Days/Times** for when assessments can be scheduled.
- **Room Schedule:** Establish a separate calendar for room reservations. If there are any organizations or individuals that site space must be shared with, ensure those individuals are informed and there are no conflicts for space/scheduling.
- **Reserve Room:** Send email to the research space coordinators with room you are booking, Date, Times, and project for which the assessment room will be needed.
- **Parking:** Ensure all parking has been reserved for participants upon day and time of their visit.
- **Site Calendar:** Add Assessment to site Lab Calendar (Include Location, subject ID, and who is doing the assessment, in addition to any special notes : first time dx, needs ADOS, does not need ADOS, etc.)

ERP (30 minutes)

- Assessment/CASS and ERP are often scheduled on the same day for visits.
- ERP should be scheduled along the needs and requirements of the site EEG lab performing the ERP task – make sure to have a mutual calendar you can access for the purpose of scheduling appointments.
- **Immediately confirm with site EEG team of the scheduled date.**

CASS (30 minutes)

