##### **Aim 1: To Assess Preliminary Effectiveness via Target Engagement of Social Salience.**

Hyp 1.1. Adults with ASD in the EXP group will demonstrate significantly faster growth in IMF (primary DV), CMF (secondary DV) or WMS-F (secondary DV) than adults with ASD in the WLC group, verifying the intervention had predicted effect on the target.

**Statistical Analysis:** IMF is the primary DV because it uses the same procedure, stimuli, and metric that was used with our previous successful efficacy demonstrations of SENSE Theatre. The CMF and WMS-F are measures of the same constructs on which SENSE Theatre had effects in children and adolescents, but are measured with procedures appropriate for adults. Thus, the latter two variables are considered secondary. The effect on the primary and secondary dependent variables will be tested in separate analyses for posttest and follow-up measures. In each analysis, we will use multiple linear regression in which group (experimental = EXP or waitlist control = WLC) is analyzed as the dummy-coded independent variable, and the baseline (pre-intervention) variable is analyzed as a covariate (assuming homogeneity of slopes assumption is met). By including the baseline value as a covariate, the coefficient for group becomes the between-group (EXP vs. WLC) difference in the pre-test adjusted posttest (or follow-up) scores (i.e., a measure of change similar to residualized gain scores). This method is often superior to a method that uses raw change scores directly because it improves the statistical power of the significance test and improves the accuracy of effect size estimates relative to between-group differences in raw change scores . If significant difference between groups are detected on other baseline variables that correlate with the outcome, those baseline variables will also be controlled in the multiple linear regression model, assuming appropriate assumptions are met. We will assess the homogeneity of slopes assumption by testing the interaction effect between baseline variable and treatment group assignment. If there is a significant interaction, then we will assess the treatment effect at various levels of the pre-intervention variable. If other regression assumptions (e.g., homoscedasticity, normality of residuals) are not met, robust standard error estimates will be used to test parameters in analogous models.

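### Separate posttest and follow-up regressions drop anyone lost after posttest from the follow-up comparison, which can bias that estimate modestly, in either direction, if loss depends on posttest response

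*SAP*

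**What the plan says.** The sample-size paragraph of SAP section 4.4 is headed "Post-attrition Sample Size Used to Test Aims and Compute Statistical Power", and it closes with "The analyses and power analyses are based on post-attrition sample size and past findings involving the primary dependent variables". It plans for a recruited and an enrolled number ("We propose to recruit approximately 46 participants to enroll 40 participants over the first 2 years of the project") and for loss ("Using a 10% attrition rate, which is the maximum attrition rate to date of past SENSE Theatre trials"). It does not say which visit defines the post-attrition sample.

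Under Aim 1, Hyp 1.1: "The effect on the primary and secondary dependent variables will be tested in separate analyses for posttest and follow-up measures". Each analysis is a linear regression on arm with the baseline value of the same variable as covariate. Other baseline variables are added if they are imbalanced and related to outcome. The posttest value is not in the follow-up model. Aim 2 uses the same model for Hyp 2.1 and also tests its associations separately at the two visits.

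The Protocol (Research Components) places follow-up 2.5 months after the post visit and offers the waitlist arm its programme only after all study visits. Follow-up is thus still a comparison of treated with untreated participants, and there is time to lose people between the two visits.

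**The concern.** Someone with baseline and posttest data but no follow-up value is absent from the follow-up regression, and the posttest value is not used to stand in for what is missing. Baseline adjustment protects the comparison when loss depends on arm and baseline score only. It does not protect it when people leave because of how they responded by posttest. If EXP participants who gained little tend to leave, the remaining EXP group looks better than the randomised one; other patterns push the estimate the other way.

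Three elsewhere-stated methods do not help. The robust standard errors under Aim 1 deal with unequal variance and non-normal residuals. The generalized estimating equation under Aim 2 is exploratory and has no stated treatment term. The growth model under Future Directions is for a later, larger trial.

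At stake is a one-tailed test, without alpha adjustment, whose results are meant to inform a go/no-go decision.

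**Working it through.** **1. The plan's own figures reproduce.** With 20 per arm, one-sided 5% and 80% power, the noncentral t (38 df) gives a minimal detectable difference d = 0.801. R² = d²/(d² + 4) = 0.642/4.642 = 0.138. The SAP states 0.80 and 0.14. For attrition, 40/0.90 = 44.4 and 46 × 0.90 = 41.4, so a target of 40 after 10% loss is reasonable. The SAP also uses 40 for the number enrolled; on that reading 40 × 0.90 = 36 remain.

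**2. Precision.** If 10% of 40 were lost after posttest (36 left, 18 per arm), the follow-up detectable difference rises to 0.846 (R² = 0.152). Power falls from 79.9% to 76.0% at d = 0.80, and from 89.9% to 86.8% at d = 0.94.

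**3. Bias with no true effect: assumptions.** None of these is in the documents except the rough 10% loss.
- 44 randomised, 22 per arm; 4 lost after posttest (4/44 = 9.1%).
- Posttest/follow-up correlation 0.7; baseline correlation r with each later visit 0.3 to 0.55.
- EXP loss tied to low posttest score; any waitlist loss random; splits from 4 + 0 to 2 + 2.

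**4. Hand formula.** If k EXP participants are lost and average m SD below their arm's mean at posttest, the retained mean shifts by k·m/(22 − k). The part carried into the baseline-adjusted follow-up score is (0.7 − r²). So bias ≈ (0.7 − r²) × m × k/(22 − k). Solving for m:
- Bias 0.10, r = 0.3, k = 4: m = 0.10 × 18/(0.61 × 4) = 0.74 SD.
- Bias 0.16, r = 0.3, k = 4: m = 0.16 × 18/(0.61 × 4) = 1.18 SD.
- Bias 0.02, r = 0.55, k = 2: m = 0.02 × 20/(0.3975 × 2) = 0.50 SD.

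**5. Simulation under the same assumptions.**
- Log-odds slope 0.75 to 1 per SD: bias about 0.02 to 0.10 SD, one-tailed false-positive rate about 6 to 10%.
- Slope 2, all 4 losses in EXP, r = 0.3: about 0.16 SD.
- The four lowest EXP scorers always leave (a limiting case): about 0.20 SD at r = 0.3, and 0.14 SD at baseline correlations of 0.5 to 0.6.
- Random loss: near zero, 5%.
- Sampling SD of the estimate: about 0.27 to 0.31.

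Check on the error rate: 0.02/0.27 = 0.07 gives P(Z > 1.645 − 0.07) = 5.8%, and 0.10/0.31 = 0.32 gives P(Z > 1.645 − 0.32) = 9.3%. Both agree with the simulation.

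**6. Direction, with a true follow-up difference of 0.80 SD.** This run has 20 per arm, baseline correlations 0.6 (posttest) and 0.5 (follow-up), posttest/follow-up correlation 0.6 to 0.8, and slopes 0.75 to 1.5. Loss depends on posttest in the same direction in both arms, in one arm only, or in opposite directions. The planned regression averages 0.75 to 0.93 at 10% loss and 0.73 to 1.04 at 20%. The shift is therefore −0.05 to +0.13 SD, and −0.07 to +0.24 SD. An estimator that uses the posttest value averages 0.79 to 0.81 throughout.

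**7. Limit of the remedy.** When loss depends on the unseen follow-up value itself, the joint model keeps most of the bias: 0.08 SD against 0.12 SD for the planned regression.

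**The case against.** The case for leaving the plan alone has real substance.

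- *The sentence is planning language.* It speaks of a sample size and past findings and does not define an analysis set. A reader might infer an explicit completers-only rule; the wording does not go that far. Part of the SAP was also unavailable for this review, so a missing-data statement there cannot be excluded. What stands is narrower: the separate regressions, as written, cannot use a participant who has no follow-up value.
- *The documents give no sign that loss will depend on response.* A reader might infer unequal motives to stay from the Protocol's scheduling points ("Intervention will be free upon completion of all 4 parts (pre, midpoint, post, and follow-up"). That line is addressed to all participants and does not distinguish the arms. The waitlist statement in Research Components can be read as timing only. Loss that differs by arm alone would not bias the regression in any case.
- *The loss is small.* The 10% is the highest rate seen in past trials and covers the whole trial. The scenarios here put all of it between posttest and follow-up, which is unfavourable.
- *This is a pilot.* The SAP says its results will be treated as such and accepts type 1 error inflation. It anchors power on a posttest effect. That lowers the stakes, but it does not justify a bias that data already collected could reduce.

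**Conclusion.** The point holds in a limited form. Participants lost between posttest and follow-up contribute nothing to the follow-up comparison, and the estimate can then be biased in either direction if loss depends on posttest response. Under moderate selection and about 10% loss, the bias is roughly a third of a sampling SD at most (0.10/0.31 = 0.32). The loss of power is of similar concern. About 0.16 SD or more in the null scenarios needs strong selection confined to EXP and a low baseline correlation.

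It would be too strong to say that the randomised comparison at follow-up is broken, or that a joint model makes it safe. The correlations, selection strengths and number randomised are assumptions, so the figures show direction and range, not a forecast. The planned power calculation is not in error. The change is worth making because it is cheap, not because the plan is unsound.

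**What to change.** State that all randomised participants are analysed in their assigned arm, and say what post-attrition means at each visit. For each outcome, fit one likelihood-based repeated-measures model to baseline, posttest and follow-up. Add midpoint for SRS-2, ABAS and ABCL, which the Protocol collects then. Use arm-by-visit terms and small-sample degrees of freedom, and take the posttest and follow-up contrasts from that model. Multiple imputation that includes the posttest value is an equivalent route. Keep the planned baseline-adjusted regression in completers as a sensitivity analysis. Add one simple analysis for loss that depends on unseen follow-up values, for example by shifting the imputed values of those lost over a stated range.

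The cost is a revised SAP paragraph and slightly more analysis work, with no new visits, data or participants. The gain for the posttest test of IMF is small, because IMF has no midpoint value. The benefit is mainly at follow-up.
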